#### 7.2.4. Overdose

##### 7.2.4.1. Definition of Overdose

Overdose, as defined for this protocol, refers to azacitidine and durvalumab dosing only.

On a per dose basis, an overdose is defined as any amount over the protocol-specified dose of subcutaneous azacitidine or intravenous durvalumab assigned to a given subject, regardless of any associated AEs or sequelae.

On a schedule or frequency basis, an overdose is defined as any amount more frequent than the protocol-required schedule or frequency. On an infusion rate basis, an overdose is defined as any rate faster than the protocol-specified rate.

- For subcutaneous azacitidine, any amount over the protocol-specified dose
- For IV durvalumab, 10% over the protocol-specified dose.

#### **7.2.4.2. Actions Taken in the Event of an Overdose**

Complete data about drug administration, including any overdose, regardless of whether the overdose was accidental or intentional, should be reported in the case report form. See Section 10.1 for the reporting of AEs associated with overdose.

Use of IP in doses in excess of that specified in the protocol is considered to be an overdose. There is currently no specific treatment in the event of overdose of IP, and possible symptoms of overdose are not established.

An overdose with associated AEs will be recorded as the AE diagnosis or symptoms in the relevant AE modules of the eCRF and in the Overdose eCRF module.

An overdose without associated symptoms will only be reported in the Overdose eCRF module.

If an overdose of durvalumab occurs in the course of the study, then the Investigator or other site personnel will inform appropriate Celgene representatives immediately, or no later than 24 hours of when he or she becomes aware of it. The designated Celgene representative will work with the Investigator to ensure that all relevant information is provided to Celgene.

For overdoses associated with an SAE, the standard reporting timelines apply, see Section 10.5.

For other overdoses, reporting must occur within 30 days.

#### **7.2.5. Discontinuation**

Reasons for discontinuing a subject from the investigational product and/or from the study are listed in Sections 11.1 and 11.2.

Because a hematologic response to treatment with subcutaneous azacitidine may be delayed, it is recommended that subjects receive at least 6 cycles of treatment with the IP; however, subjects may be discontinued from treatment at the Investigator's discretion prior to reaching the recommended minimum number of cycles for any of the reasons detailed above. The reason for discontinuation should be recorded in the subject's eCRF and source documents.

### **7.3. Method of Treatment Assignment**

Subjects will be enrolled via IRT to ensure timely registration and to facilitate subject tracking and IP resupply needs.

Investigator or designated site staff will be assigned password protected, identification numbers that give them authorization to call into the IRT to enroll a subject. At screening, the Investigator or designated staff will call into the IRT and provide the requested identifying information for the subject. The IRT will then confirm the assignment of a unique subject number. If a subject is screened but not enrolled, the screen-failure must be registered using the IRT. During the

treatment phase, calls will be placed to the IRT for each new allocation of IP to a subject, to acknowledge receipt of additional IP shipments to the site, and to register changes in a subject's status (eg, drug hold, dose modification, or treatment discontinuation). Details regarding use of the IRT are found in the IRT User Manual.

#### **7.4. Packaging and Labeling**

The label(s) for IP will include sponsor name, address and telephone number, the protocol number, IP name, dosage form and strength (where applicable), amount of IP per container, lot number, expiry date (where applicable), medication identification/kit number, dosing instructions, storage conditions, and required caution statements and/or regulatory statements as applicable. Additional information may be included on the label as applicable per local regulations.

No blinding is applied in this study.

#### **7.5. Investigational Product Accountability and Disposal**

The Investigator(s) or designee is responsible for taking an inventory of each shipment of investigational product received and comparing it with the accompanying shipping order/package slip. The investigator(s) will verify the accuracy of the information on the shipping order/package slip and call IRT to register receipt at the site of the investigational product.

At the study site, investigational product will be stored in a locked, safe area to prevent unauthorized access and should be stored as directed on the product label.

An accurate accounting of the dispensing and return of investigational product for each study subject will be maintained in source documents on an ongoing basis by a member of the study site staff. Additionally, if any investigational product is lost or damaged or if the study subject misses a dose, this information should be documented in the study subject's eCRF and source documents.

Investigational product accountability will be assessed by the Investigator or designee. Applicable information such as lot number, vial count, and expiration date should be collected.

The investigator(s) or designee(s) is responsible for accounting for all IP during the course of the study according to applicable regulatory requirements. Any unused IP must be retained by the investigative site for accountability to be conducted by a Celgene representative (or designee). If any IP is lost or damaged, its disposition should be documented. At periodic monitoring visits, a Celgene representative (or designee) will conduct IP accountability and address any discrepancies. At the conclusion of the study, all remaining IP will be counted, reconciled with dispensing records, documented, and destroyed at the clinic site or allocated drug destruction location after completion of drug accountability by a Celgene representative (or designee). The Celgene representative (or designee) will ensure that a final report of drug accountability to the unit dose level be prepared and placed in both the Investigator study file and the central clinical study file.

A copy of the site's Standard Operating Procedure (SOP) for drug destruction may be collected by the sponsor (or designee). Any revisions to a site's destruction process must be provided and

approved by the sponsor (or designee) prior to implementation of this protocol. Any site without a sponsor (or designee)-approved destruction SOP and process will be required to return IP to Celgene.

Celgene (or designee) will review with the Investigator and relevant site personnel the process for Investigational Product return, disposal, and/or destruction including responsibilities for the site versus Celgene (or designee).

## **7.6. Investigational Product Compliance**

Subjects will receive azacitidine and durvalumab at the investigation site during the study. Administration of all IP will be recorded by the Investigator on the subject's eCRF, including dispensing, dosing, and any changes in dosage administration such as interruption or reduction in dosing due to an AE.

## 8. CONCOMITANT MEDICATIONS AND PROCEDURES

All prior and concomitant medications (prescription and nonprescription), treatments, and therapies taken from signing of the ICF up to 28 days after the last dose of subcutaneous azacitidine or up to 90 days after the last dose of for durvalumab, or up to the Treatment Discontinuation Visit, whichever date is later, must be recorded on the appropriate subject's eCRF.

All prior treatments for MDS, including ESAs, thrombopoiesis-stimulating agents (TSAs), iron-chelating agents, or other medications considered supportive care for MDS should be recorded on the respective subject's eCRF(s) regardless of the date of these treatments. All prior treatments for AML, as applicable, should also be recorded on the appropriate subject's eCRF(s).

Concomitant medications should be kept to a minimum during the study. However, if considered necessary for the subject's welfare and are unlikely to interfere with the IP, they may be given at the discretion of the Investigator.

### 8.1. Permitted Concomitant Medications and Procedures

Best supportive care may be used in combination with study therapy if deemed necessary. Best supportive care for this study includes, but is not limited to, treatment with RBC or whole blood transfusions, fresh frozen plasma transfusions, single donor or pooled donor platelet transfusions, antibiotic, antiviral and/or antifungal therapy, nutritional support as needed, and myeloid growth factors (G-CSF and granulocyte colony stimulating factor [GM-CSF]) for subjects experiencing neutropenic infections. The use of myeloid growth factors is also allowed for secondary prophylaxis under certain conditions as described below. The use of these products will be considered as concomitant treatment and documented as concomitant medications, therapies or procedures.

Blood product support (RBCs and platelets) may be administered according to institutional standards. Red blood cell and platelet transfusions will be considered concomitant procedures and should be collected on the appropriate subject's eCRF.

Subjects who are currently using iron-chelating agents should be on a stable or decreasing dose for at least 8 weeks (56 days) prior to randomization. Initiation, modification, and/or discontinuation of iron-chelating agents during the treatment phase of the study is discouraged and should be discussed with the sponsor's medical monitor first whenever possible.

Subjects may be administered supportive and palliative care (eg, pain control) as clinically indicated throughout the study.

It is recommended that an antiemetic medication such as a serotonin 5-HT3 receptor antagonist (eg, ondansetron) be taken 30 minutes prior to IP administration during Cycle 1. If nausea/vomiting is not significant, further antiemetic prophylaxis may not be needed. Pretreatment or posttreatment with a serotonin 5-HT3 receptor antagonists, or other locally available and appropriate antiemetic medication, will be considered concomitant treatment and should be recorded on the appropriate subject's eCRF.

Treatment with antidiarrheal medications is recommended at the first sign of diarrhea. Premedication with antidiarrheal medication for subsequent doses of subcutaneous azacitidine

and/or durvalumab may be appropriate. Pre and posttreatment with an antidiarrheal must be recorded in the subject's eCRF as concomitant medication.

Myeloid growth factors (G-CSF and GM-CSF) may be given per Investigator's discretion for the treatment of neutropenic fever/infections as well as for secondary prophylaxis if the subject had a previous event of neutropenic fever/infection or neutropenia Grade 4 during the treatment phase of the study and the safety of the subject is considered jeopardized by subsequent episodes of neutropenic fever/infections or Grade 4 neutropenia.

For subjects who develop an ANC  $< 0.5 \times 10^9/L$  (or per institutional standards), administration of prophylactic fluoroquinolone antibiotics (eg, ciprofloxacin or levofloxacin) or other recognized prophylactic antibiotics may be considered and documented as a concomitant medication on the appropriate subject's eCRF. If neutropenic fever/infection occurs, treatment should consist of a broad spectrum antibiotic, and if the Investigator deems the use of a myeloid growth factor to be medically important, myeloid growth factors may also be administered. For secondary prophylaxis with myeloid growth factors, the dose modification guidelines detailed in Section 7.2.2 remain applicable. Discontinuation of secondary prophylaxis with myeloid growth factors should be considered by the Investigator as clinically appropriate.

Concurrent systemic corticosteroids for non-cancer-related conditions are allowed (eg, insulin for diabetes and hormone replacement therapy), provided the subject is on a stable or decreasing dose for  $\geq 1$  week prior to the first dose of IP, and provided the exclusion criteria #17 is met. Initiation, modification, and/or discontinuation of corticosteroids during the treatment phase of the study is discouraged and should be discussed with the sponsor's medical monitor first whenever possible.

For AML subjects, the use of hydroxyurea is permitted up to 2 weeks prior to the screening hematology sample and is prohibited during the whole study participation.

## 8.2. Prohibited Concomitant Medications and Procedures

Best supportive care for this study specifically excludes cancer surgery, immunotherapy, biologic therapy, radiotherapy, anticancer hormonal therapy, and systemic chemotherapy where the goal is to eradicate or slow the progression of the disease.

The following concomitant medications are specifically **prohibited** during the course of the study:

- Cytotoxic, chemotherapeutic, targeted, or investigational agents/therapies
- Azacitidine for IV injection, decitabine, or other demethylating agents
- Lenalidomide, thalidomide, and a proprietary series of drugs with immunomodulatory and other properties (IMiDs®)
- Erythropoiesis stimulating agents and other hematopoietic growth factors (eg, interleukin-3)
- Romiplostim and other TSAs (eg, interleukin-11, eltrombopag)
- Hydroxyurea for MDS subjects only (for AML subjects, see Section 8.1),
- Androgens, unless to treat hypogonadism

- Oral retinoids (topical retinoids are permitted)
- Arsenic trioxide
- Interferon
- Immunosuppressive medications including, but not limited to systemic corticosteroids at doses exceeding 10 mg/day of prednisone or equivalent, methotrexate, azathioprine, and tumor necrosis factor – alpha (TNF- $\alpha$ ) blockers. Use of immunosuppressive medications for the management of investigational product-related AEs or in subjects with contrast allergies is acceptable. In addition, use of inhaled, topical, intranasal corticosteroids or local steroid injections (eg, intra-articular injection) is permitted. Temporary uses of corticosteroids for concurrent illnesses (eg, food allergies, CT scan contrast hypersensitivity, moderate to severe infusion-related reactions, etc) are acceptable upon discussion and agreement with the sponsor's medical monitor.
- Live attenuated vaccines during the study through 30 days after the last dose of durvalumab.

Refer to Section 4.2.2 for exclusion criteria pertaining to prohibited concomitant medications.

### 8.3. Required Concomitant Medications and Procedures

There are no required concomitant medications, although prophylactic treatment with an antiemetic and/or antidiarrheal medication may be considered and is recommended during the first cycle.

## 9. STATISTICAL CONSIDERATIONS

### 9.1. Overview

This is a Phase 2 randomized, multicenter, open-label, study evaluating the efficacy of subcutaneous azacitidine in combination with durvalumab in the defined study population (see Section 4).

The study will be run in two separate, parallel cohorts with separate inclusion and exclusion criteria as well as separate response criteria (MDS and AML).

Subjects in each cohort will be randomized into a monotherapy arm and a combination therapy arm with 1:1 allocation ratio using dynamic randomization method. At randomization, subjects will be stratified by cytogenetic risk (Intermediate risk versus poor risk for AML cohort, very good, good and intermediate risk versus poor and very poor risk for MDS Cohort). In each cohort, the study will be conducted in two stages, with an interim analysis for futility purposes following completion of the first stage and the primary analysis following completion of second stage. The interim analysis for futility will be performed independently in each cohort, and there will not be any recruitment hold between stages within each cohort.

The primary objective is to evaluate the efficacy of subcutaneous azacitidine in combination with durvalumab as compared with subcutaneous azacitidine alone in the defined study population (see Section 4). The secondary objectives are to assess the safety and tolerability of subcutaneous azacitidine in combination with durvalumab; to assess overall survival, and additional secondary efficacy criteria including but not limited to time to response, duration of response, cytogenetic responses, proportion of MDS subjects transforming to AML and time to AML transformation, and duration of remission in AML subjects; to evaluate the PK profile of durvalumab in combination with subcutaneous azacitidine; CCI

This section defines the subject populations for the statistical data analyses, the justifications of sample sizes for each cohort, and the methodologies that will be used for the efficacy and safety analyses. All statistical analyses specified in this protocol will be conducted using SAS® Version 9.2 or higher unless otherwise specified.

### 9.2. Study Population Definitions

For the purpose of statistical analyses and data presentation, the study populations are defined as follows.

#### 9.2.1. Intent-to-Treat Population

The intent-to-treat (ITT) population will include all randomized subjects. The primary efficacy analyses will be performed on the ITT population.

#### 9.2.2. Efficacy Evaluable Population

The supportive efficacy analyses will be performed on the efficacy evaluable (EE) population, which will include all ITT subjects who completed 6 cycles of treatment, unless they have

established an earlier response or who discontinued the study due to death or disease progression.

Subjects who do not have an on-treatment disease assessment and discontinue due to death or disease progression without postbaseline response assessment will be considered as nonresponders.

### 9.2.3. Safety Population

The safety population will include all subjects who take at least 1 dose of IP.

### 9.2.4. Pharmacokinetic Population

The PK population includes all subjects who received at least one dose of study treatment and who have at least 1 measurable durvalumab concentration datum. For subjects who are determined to be noncompliant with respect to administration of durvalumab, or for subjects with incomplete data, a decision as to their inclusion in the population will be made on a case-by-case basis prior to the analysis.

## 9.3. Sample Size and Power Considerations

### 9.3.1. Myelodysplastic Cohort

Sekeres et al. (Sekeres, 2014) demonstrated that treating subjects with higher-risk MDS resulted in an ORR (CR, mCR, PR, HI) of 36% after four cycles of azacitidine monotherapy. This number is consistent with the “HI and better” rate from the AZA-MDS-001 trial of 36.4%. Assuming a treatment effect of 100% relative improvement of ORR (from 36% to 72% ORR), a sample size of 72 subjects will provide a power of 90% to detect such an effect at the 5% level of statistical significance.

An interim analysis for futility purpose will be conducted on the first 30 subjects who have completed 6 cycles of treatment unless they have established an earlier response (i.e. for arm A, 6 cycles of durvalumab and azacitidine, arm B, 6 cycles of azacitidine) or discontinued due to death or disease progression. The MDS cohort will be completed to include a total of 72 efficacy evaluable MDS subjects if one of the below conditions is met:

- If the overall response rate (considering the composite score of CR + PR + mCR + HI) in the combination arm is numerically higher than or equal to the control group (azacitidine alone) or,
- If the response rate of one of the components of this composite score (in particular CR rate) in the combination arm is numerically higher than or equal to the control group (azacitidine alone) or,
- If evidence of a clinical meaningful difference in favor of the combination arm in a secondary endpoint (eg, duration of response) is provided.

If none of these conditions is met, then the cohort might be terminated. The DMC will review the data at the time of interim analysis and will provide recommendation/advice to Celgene.

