The interim analysis on futility will support early assessment of efficacy and may minimize the number subjects exposed to the investigational regimen in the absence of signs of efficacy.

The combination of azacitidine and durvalumab is currently being evaluated in other studies. Currently there is no evidence for drug interactions in terms of dosing or overlapping toxicity. The combination of azacitidine with other PD-1 inhibitors (nivolumab, pembrolizumab) and PD-L1 inhibitors (atezolizumab) are under clinical investigation.

The azacitidine dosing schedule for MDS and AML is identical (as per the EU approved dosing regimen). Due to the similar nature of MDS and AML in terms of toxicity, dose regimens will be identical in both disease cohorts.

CCI

[REDACTED]

CCI [REDACTED]

[REDACTED]

[REDACTED]

[REDACTED]

CELGENE PROPRIETARY INFORMATION

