For toxicity that is thought to be related to treatment with durvalumab, including immune-mediated adverse events (imAEs) or infusion-type reactions, as well as for nonimmune mediated reactions, the infusion of durvalumab may be slowed or interrupted, or a dose may be withheld, as described in Section 7.2.2.2. Dose reduction of durvalumab is not permitted.

In the event that a subject assigned to the combination treatment arm discontinues treatment with durvalumab or subcutaneous azacitidine because of drug-related toxicity, treatment with subcutaneous azacitidine or durvalumab monotherapy may continue until a discontinuation criterion is met (see Section 11.1). These subjects will be included in the ITT, safety and EE populations if they meet the respective criteria.

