### 9.3.2. Acute Myeloid Leukemia Cohort

Dombret and Fenaux (Dombret, [2015]; Fenaux, [2010]) showed the response (CR + CRi) rate is 25% in AML subjects treated with azacitidine. Assuming a treatment effect of 100% relative improvement of CR (from 25% to 50% absolute CR rates), a sample size of 110 subjects will provide a power of 80% to detect such an effect at the 5% level of statistical significance.

An interim analysis for futility purpose will be conducted on the first 50 subjects who have completed 6 cycles of treatment unless they have established an earlier response (i.e. for arm A, 6 cycles of durvalumab and azacitidine, arm B, 6 cycles of azacitidine) or discontinued due to death or disease progression. The AML cohort will be completed to include a total of 110 efficacy evaluable AML subjects if one of the below conditions is met:

- If the overall response rate (considering the composite score of CR + CRi) in the combination arm is numerically higher than or equal to the control group (azacitidine alone) or,
- If the response rate of one of the components of this composite score (in particular CR rate) in the combination arm is numerically higher than or equal to the control group (azacitidine alone) or,
- If evidence of a clinical meaningful difference in favor of the combination arm in a secondary endpoint (eg, duration of response) is provided.

If none of these conditions are met, then the cohort might be terminated. The DMC will review the data at the time of interim analysis and will provide recommendation/advice to Celgene.

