## 9.8. Interim Analysis

Interim analyses for futility purposes are planned for each cohort as described in Section 9.3. and will be based on the EE population.

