14. INTERIM ANALYSIS

14.1. General Information

The interim analysis on futility will support early assessment of efficacy and may minimize the number of subjects exposed to the investigational regimen in the absence of signs of efficacy.

An interim analysis for futility purposes following the completion of first stage will be conducted. The primary analysis will be conducted following the completion of second stage. The decision to proceed to Stage 2 after completion of Stage 1 will be performed independently in each cohort as mentioned below.

The DMC will review the safety data on a regular basis.

Myelodysplastic Cohort

An interim analysis for futility purpose will be conducted on the first 30 subjects who have completed 6 cycles of treatment unless they have established an earlier response (CR, mCR, PR or HI) or discontinued due to death or disease progression. Subjects assigned to Arm A, who received less than 3 cycles of durvalumab and continued under azacitidine monotherapy are to be excluded from the interim analysis.

The MDS cohort will be completed to include a total of 72 MDS subjects. Details of futility rules are given in [section 4.3.1](#).

Acute Myeloid Leukemia Cohort

An interim analysis for futility purpose will be conducted on the first 50 subjects who have completed 6 cycles of treatment unless they have established an earlier response (CR or CRi) or discontinued due to death or disease progression. Subjects assigned to Arm A, who received less than 3 cycles of durvalumab and continued under azacitidine monotherapy are to be excluded from the interim analysis.

The AML cohort will be completed to include a total of 110 AML subjects. Details of futility rules are given in [section 4.3.2](#).

Interim analyses for futility purposes are planned for each cohort as described above and will be based on the EE population.

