17.2. International Working Group (IWG) Response Criteria in Myelodysplasia (Cheson, 2006)

Altering Disease Natural History	
Complete remission (CR)	
 ▪ BM Blasts \leq 5% 
AND
 
 ▪ All of the following peripheral blood values met: 
 ▪ Hemoglobin \geq 11 g/dL ▪ Platelets \geq 100 x10⁹/L ▪ ANC \geq 1.0 x10⁹/L ▪ Peripheral Blasts=0% 
Labs must meet criterion for at least 28 consecutive days. If not confirmed for 28 days then response should be mCR.
 
In addition
 
 ▪ The 7/3 rule should be applied to Hemoglobin. ▪ Platelets collected 3 days period following Platelet transfusion will not be used - ANC values that must be at least 14 days following a G-CSF application
Partial remission (PR)	
 ▪ BM Blasts decreased by \geq 50% over pretreatment but still $>$ 5% 
AND
 
 ▪ All of the following peripheral blood values met: 
 ▪ Hemoglobin \geq 11 g/dL ▪ Platelets \geq 100 x10⁹/L ▪ ANC \geq 1.0 x10⁹/L ▪ Peripheral Blasts=0% 
Labs Must meet criterion for at least 28 consecutive days.
 
In addition
 
 ▪ The 7/3 rule should be applied to Hemoglobin. ▪ Platelets collected 3 days period following Platelet transfusion will not be used 
ANC values that must be at least 14 days following a G-CSF application

Marrow CR	
 ▪ Bone marrow: $\leq 5\%$ myeloblasts and decrease by $\geq 50\%$ over pretreatment with baseline BM blast $>5\%$ 
AND
 
 ▪ Not all of the following peripheral blood values met or none are met: 
 ▪ Hemoglobin ≥ 11 g/dL ▪ Platelets $\geq 100 \times 10^9/L$ ▪ ANC $\geq 1.0 \times 10^9/L$ ▪ Peripheral Blasts=0% 
Peripheral blood: if HI responses, they will be noted in addition to marrow CR

Stable disease (SD)	Any evaluable time point where criteria for all other response categories (i.e., CR, PR, PD, Failure due to death, Not Assessable) are not met
Failure	Death during treatment

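### Read literally, the MDS futility rule rarely permits stopping; separately, the protocol and SAP define the Arm A interim set differently

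*Protocol*

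**What the plan says.** **The rule.** Protocol 9.3.1 and SAP 4.3.1 complete the MDS cohort to 72 if any one of three conditions is met:

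- the combination ORR (CR + PR + mCR + HI) is at least equal to control;
- the rate for "one of the components of this composite score (in particular CR rate) in the combination arm is numerically higher than or equal to the control";
- a secondary endpoint shows a clinically meaningful difference, with no threshold given.

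If all three fail, the cohort might be terminated, on DMC advice. Protocol 9.3.2 and SAP 4.3.2 apply the same rule to AML with two components, CR and CRi.

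**Its purpose.** Protocol 1.5.5 gives the purpose as limiting exposure "in the absence of signs of efficacy". SAP 14.1 says that the look "may minimize the number of subjects exposed to the investigational regimen in the absence of signs of efficacy".

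**The interim set.** Protocol 9.3.1 and 9.3.2 take the first 30 (MDS) or 50 (AML) subjects who completed 6 cycles, spelled out as "for arm A, 6 cycles of durvalumab and azacitidine, arm B, 6 cycles of azacitidine", unless they responded earlier, died or progressed. Protocol 9.8 adds: "Interim analyses for futility purposes are planned for each cohort as described in Section 9.3. and will be based on the EE population". The EE definition in protocol 9.2.2, "which will include all ITT subjects who completed 6 cycles of treatment", does not say which drug's cycles count. Of Arm A subjects who stop one drug, protocol 3.2.2 says "These subjects will be included in the ITT, safety and EE populations if they meet the respective criteria".

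The SAP (4.1, 4.3.1, 4.3.2, 5.2.2, 14.1) has no 6-cycle durvalumab requirement. It excludes Arm A subjects who had fewer than 3 durvalumab cycles and continued azacitidine alone.

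**The concern.** With about 15 subjects per arm and four components, the combination will nearly always tie or lead on at least one of them, even when it is behind overall. A criterion that nearly always says continue tells the DMC little, and it does not serve the stated purpose of limiting exposure. The third condition can only make stopping rarer.

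The second problem is separate. With 30 subjects and a rule that can turn on a single tie, two definitions of who is counted can give two answers from the same data.

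**Working it through.** **1. The plan's own figures.** Unpooled two-sided formula: n per arm = (z0.975 + z_power)² × [p1(1−p1) + p2(1−p2)] / (p1−p2)².

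- MDS: 10.51 × (0.2304 + 0.2016) / 0.1296 = 35.0, so 36 per arm and 72 in total.
- AML: 7.85 × (0.1875 + 0.25) / 0.0625 = 54.9, so 55 per arm and 110 in total.

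Both sample sizes reproduce. Neither document gives an operating characteristic for the futility rule.

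**2. Inputs for the rule.** From the documents: control ORR 36% (MDS) and 25% (AML); 30 and 50 subjects at the look; 1:1 allocation, hence 15 v 15 and 25 v 25. Assumed, because the documents give no component rates:

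- MDS splits of 36 points into CR/PR/mCR/HI-only: 9/9/9/9, 15/2/9/10, 10/5/11/10.
- AML splits of 25 points into CR/CRi: 12.5/12.5, 15/10, 20/5, 22/3, 5/20.

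SAP 17.2 lets HI coexist with marrow CR ("if HI responses, they will be noted in addition to marrow CR"). I therefore also let 50-100% of CR/PR/mCR responders have HI, and added the splits 12/12/12/0 and 14/8/10/4. Condition 3 is ignored.

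**3. One case by hand.** Suppose the combination has no responders and the exclusive split is 9/9/9/9. Stopping is permitted only if control has at least one responder in every component:

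1 − 4(0.91)¹⁵ + 6(0.82)¹⁵ − 4(0.73)¹⁵ + (0.64)¹⁵ = 1 − 0.972 + 0.306 − 0.036 + 0.001 = 29.9%.

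In the other 70% of looks a 0 v 0 component says continue.

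**4. Probability that stopping is permitted.** Stop if the combination is strictly below control on ORR and on every counted component. Exact enumeration, except unequal arms (simulation).

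| Reading | No effect | ORR halved | No combination responders |
|---|---|---|---|
| MDS, HI overlapping, 15 v 15 | 1.5-3.5% | 6-18% | 17-61% |
| MDS, exclusive components, 15 v 15 | 0.5-0.8% | 3-6% | 13-30% |
| MDS, overlap and unequal arms (14:16 to 13:17, either way), upper limit | 12% | 37% | 69% |
| MDS, only ORR or CR counts | 22-26% | 49-59% | 76-91% |
| MDS, ORR alone | 42.5% | 82% | >99% |
| AML, two components, 25 v 25 | 12-15% | 32-47% | 53-93% |
| AML, ORR alone | 43.5% | 83% | >99% |

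Ties at zero are only part of the cause. With exclusive components and 0 v 0 not counted, the figures are 1.9-3.4% / 17-23% / >99%, still rare when there is no effect.

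**5. The two interim sets.** SAP 5.1.3 starts a cycle at the first dose of either drug, so azacitidine cycles alone can make up 6 cycles of treatment.

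| Arm A subject | Protocol 9.3 | SAP |
|---|---|---|
| Non-responder, 3-5 durvalumab and 6 azacitidine cycles | out | in |
| Early responder, fewer than 3 durvalumab cycles, continued azacitidine | in | out |

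SAP 15 declares the under-3-cycle exclusion but not the dropped 6-cycle requirement.

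**6. Enrolment still open at the look.** Assume even accrual over 15 months (4.8 and 7.33 subjects a month), 168/30.4375 = 5.52 months for 6 cycles, and 20% non-evaluable. Protocol 9.3 completes to 72 and 110 efficacy evaluable subjects, so 90 and 137.5 are enrolled.

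- MDS: 30/0.8 + 5.52 × 4.8 = 64 enrolled at the look; (90 − 64)/2 = 13 Arm A assignments left.
- AML: 50/0.8 + 5.52 × 7.33 = 103; (137.5 − 103)/2 = about 17 left.
- A 2-month lag leaves about 8 and 10.

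**The case against.** **The percentages rest on assumed splits.** This stands. The very low exclusive-component figures should not be read alone, because SAP 17.2 allows overlap and the first 30 evaluable subjects need not divide 15 v 15. A reader might infer that the rule says continue in most looks even with no combination responders. That holds for the exclusive splits at 15 v 15 but not generally, since with overlap and unequal arms stopping is permitted in up to 69% of such looks.

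**The CR parenthesis may mean that only CR counts.** This also stands as an ambiguity. On that reading stopping is not rare. The words refer to any one component, but they do not exclude the narrower intent.

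**Keeping a Phase 2 cohort open on a CR signal is a legitimate preference, and little hangs on the rule.** Largely conceded. The rule is non-binding. Appendix O shows the DMC advising on durvalumab beyond it. The Amendment 1.0 summary expects Stage 2 to be complete by the time of the interim conclusions, and protocol 9.1 has no recruitment hold. A reader might infer damage to type I error or to the primary result; a futility-only look and an ITT primary analysis do not support that.

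**The SAP exclusion is declared.** True, so this is a partly documented change and not a hidden one. Nor are the exposure conditions one-sided in both documents: the protocol asks each arm for 6 cycles of its assigned treatment, and only the SAP's exclusion applies to Arm A alone.

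**Conclusion.** Both points hold as defects of the written text.

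On the literal reading, the MDS rule permits stopping in 0.5-3.5% of looks with no effect at 15 v 15, and in at most about 12% with overlap and unequal arms, against 42.5% for ORR alone. It therefore hardly serves its stated purpose. All of these figures depend on assumed component rates, and the CR-only reading (22-26%) remains open. It would be too strong to say that the AML rule fails too: with two components it is weakened, not disabled.

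What is lost is an informative look and possibly some durvalumab exposure. How much enrolment a sharper rule would save is uncertain: step 6 leaves 8-17 Arm A assignments per cohort, while the Amendment 1.0 summary expects none.

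The interim sets differ in both directions, and the SAP's exclusion is post-randomisation and one-sided. The effect of this on the decision cannot be sized from the documents.

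**What to change.** **Rule.** In protocol 9.3.1 and 9.3.2 and SAP 4.3.1 and 4.3.2, state that the cohort continues if combination ORR is at least equal to control ORR, and that otherwise the DMC may recommend termination. State that the rule is non-binding, and that component rates (CR in particular) and secondary endpoints go to the DMC as context and do not by themselves satisfy it.

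**Interim set.** Use one interim/EE definition in both documents, with the same condition in each arm: for example 6 cycles of azacitidine (the common drug), or earlier response, or discontinuation for death or progression. Report the two durvalumab-exposure conditions as sensitivity analyses, which keeps the sponsor's aim of adequately exposed subjects. List the dropped 6-cycle requirement in SAP 15. Any such set is still post-randomisation and belongs only to the interim and supportive analyses.

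**Editorial.** SAP 4.1 and 14.1 still make entry to Stage 2 depend on the look; align them with protocol 9.1.

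**Cost.** Wording, before the interim lock. Exact two-stage power with the SAP's Wald test (15 + 21 and 25 + 30 per arm), without and then with the ORR rule:

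- MDS v 36%: ORR 72%, 88.6 to 88.3; 60%, 54.2 to 53.8; 50%, 24.1 to 23.9.
- AML v 25%: ORR 50%, 80.2 to 79.9; 45%, 62.3 to 61.9; 37.5%, 30.6 to 30.4.

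Stopping would be permitted in 1.2% (MDS) and 2.2% (AML) of looks at the design effect. At small gains it would be permitted in 17-23% (MDS, ORR 50-46%) and 13-18% (AML, ORR 37.5-35%). A CR gain with a lower ORR would no longer give an automatic continue. If the look has already been taken, report which reading and which set were used.
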